### 1.1 Responsibilities

An Array or CRO-designated Biostatistician or Statistical Programmer will perform any statistical analyses required for patient disposition, protocol deviations, patient characteristics, efficacy and safety; an Array or CRO-designated Biostatistician is responsible for the production and quality control of all tables, figures and listings associated with these analyses. An Array or CRO-designated Clinical Pharmacology representative will perform any PK statistical analyses and is responsible for the production and quality control of all tables, figures and listings associated with these analyses. An Array Translation Science representative will perform any CCI statistical analyses and is responsible for the production and quality control of all tables, figures and listings associated with these analyses.

## 2.0 STUDY OBJECTIVES

### 2.1 Primary Objective

#### Phase 1b/Part A:

- To determine the maximum tolerated dose (MTD) and/or recommended Phase 2 dose (RP2D) of ARRY-382 in combination with pembrolizumab in patients with selected solid tumors

#### Phase 2: PD-1 or PD-L1 Inhibitor Refractory:

- To estimate the efficacy of ARRY-382 in combination with pembrolizumab in patients with advanced solid tumors following progression on prior PD-1/PD-L1 inhibitor therapy

#### Phase 2: Platinum-resistant Ovarian Cancer:

- To estimate the efficacy of ARRY-382 in combination with pembrolizumab in patients with microsatellite stable (MSS)/mismatch repair (MMR)-proficient platinum-resistant ovarian cancer (prOVCA)

#### Phase 2: Pancreatic Ductal Adenocarcinoma:

- To estimate the efficacy of ARRY-382 in combination with pembrolizumab in patients with MSS/MMR-proficient pancreatic ductal adenocarcinoma (PDA)

### 2.2 Secondary Objectives

#### Phase 1b/Part A:

- To describe the preliminary antitumor activity of the combination based on the Response Criteria In Solid Tumors, version 1.1 (RECIST v1.1)
- To describe the preliminary antitumor activity of the combination based on immune-related response criteria (irRC)
- To characterize the safety and tolerability of the combination, including acute and chronic toxicities
- To evaluate the pharmacokinetics (PK) of ARRY-382 in combination with pembrolizumab

#### Phase 2: PD-1 or PD-L1 Inhibitor Refractory:

- To further estimate the efficacy of the combination

- To estimate the efficacy of the combination, as assessed by changes in tumor markers from baseline
- To characterize the safety and tolerability of the combination, including acute and chronic toxicities
- To evaluate the PK of ARRY-382 in combination with pembrolizumab

Phase 2: Platinum-resistant Ovarian Cancer:

- To further estimate the efficacy of the combination in patients with MSS/MMR-proficient prOVCA
- To estimate the efficacy of the combination, as assessed by changes in tumor markers from baseline
- To characterize the safety and tolerability of the combination, including acute and chronic toxicities
- To evaluate the PK of ARRY-382 in combination with pembrolizumab

Phase 2: Pancreatic Ductal Adenocarcinoma:

- To further estimate the efficacy of the combination in patients with MSS/MMR-proficient PDA
- To characterize the safety and tolerability of the combination, including acute and chronic toxicities
- To evaluate the PK of ARRY-382 in combination with pembrolizumab

CC

[REDACTED]

[REDACTED]

[REDACTED]

[REDACTED]

[REDACTED]

### 3.0 INVESTIGATIONAL PLAN

#### 3.1 Overall Study Design and Plan

This is an open-label, multicenter Phase 1b/2 study to determine the MTD and/or RP2D of ARRY-382 in combination with pembrolizumab in adult patients with selected advanced solid tumors (Part A/Phase 1b); and to estimate the efficacy of the combination in patients with advanced solid tumors that have progressed on prior PD-1/PD-L1 inhibitors, in patients with proOVCA and in patients with PDA (Phase 2).

##### Phase 1b/Part A:

Part A includes a dose-escalation component with 2 planned dose cohorts (200 mg once daily [QD] and 400 mg QD). Oral doses of ARRY-382 will be administered QD in combination with pembrolizumab 2 mg/kg intravenously (iv) every 3 weeks (Q3W). Patients in Cohort 1 will be enrolled on a rolling basis up to 6 evaluable patients or until DLTs are observed in more than 1 patient during Cycle 1. If fewer than 2 of 6 patients experience a DLT during Cycle 1, patients in Cohort 2 will receive ARRY-382 400 mg QD. If 2 or more patients in Cohort 1 experience DLTs during Cycle 1, the dosage of ARRY-382 in Cohort 2 will be 100 mg QD. If a Grade 3 immune-related adverse event (irAE) (first occurrence) is reported in a given cohort, enrollment in that cohort will continue at the same dose until the toxicity is evaluated. If a second Grade 3 irAE is reported or a first Grade 3 irAE is reported in addition to a previous DLT in a given cohort, enrollment of new patients in that cohort will be stopped until the Grade 3 irAE is evaluated. If the event is not a DLT (as determined by the Investigators in consultation with the Sponsor), then enrollment may be resumed, or the cohort may be expanded to include up to 9 patients. If the Grade 3 irAE is deemed a DLT, the MTD has been achieved and additional patients will be enrolled at the previous dose level or at an intermediate dose level.

Intermediate doses and doses higher than 400 mg QD may also be considered upon review of the safety and PK results from the planned dose cohorts. In the absence of identification of an MTD, a dose of 400 mg or lower may be selected as the RP2D as long as the DLT rate is < 33% (e.g., fewer than 2 of 6 patients experience a DLT).

Part A has been completed and the MTD/RP2D of ARRY-382 was determined to be 300 mg QD in combination with pembrolizumab.

##### Phase 2

The Phase 2 part will consist of 3 separate cohorts of patients. The Phase 2 PD-1/PD-L1 Inhibitor Refractory cohort will consist of patients with advanced solid tumors who progressed on a PD-1/PD-L1 inhibitor-containing regimen as their most recent prior line of therapy are who are naïve to prior CSF-1R or CSF-1 inhibitors. The Phase 2 proOVCA and PDA cohorts will consist of

patients with prOVCA and patients with PDA, respectively, who have had at least one prior line of therapy and who are naïve to prior checkpoint inhibitor (CPI) therapy and to prior CSF-1R or CSF-1 inhibitors.

In Phase 2, at baseline, submission of archived tumor tissue from the most recent sample collection available or a fresh biopsy will be required.

All patients in Phase 2 will receive ARRY-382 at 300 mg QD, the MTD/RP2D determined during Part A, in combination with pembrolizumab 200 mg iv Q3W.

Efficacy assessments include determination of objective response using RECIST v1.1. For patients who have initial evidence of radiological progressive disease (PD) by RECIST v1.1, it will be at the discretion of the Investigator to keep a patient on study treatment or to stop study treatment until repeat imaging is performed approximately 4 weeks later in order to confirm PD per irRC. Patients with confirmed irPD should discontinue treatment. Patients with a declining Eastern Cooperative Oncology Group performance status (ECOG PS), deteriorating clinical symptoms or rapid progression of disease/progression at critical anatomical sites (i.e., central nervous system [CNS]) should be considered for treatment discontinuation based on clinical judgment.

CCI

Pharmacokinetic assessments include determination of plasma concentrations of ARRY-382 and its metabolites.

Safety assessments include monitoring of AEs, clinical laboratory tests (hematology, coagulation, clinical chemistry, thyroid panel, and urinalysis), physical examinations, vital signs, and electrocardiograms (ECGs). ECOG PS will also be assessed.

### 3.2 Sample Size Considerations

Overall, approximately 90 patients are planned for enrollment.

For Part A, the sample size of approximately 18 evaluable patients (i.e., 6 to 9 patients in each dose cohort) is standard for purposes of determining the MTD and RP2D. Patients will be considered evaluable if they receive at least 67% of protocol-specified doses of ARRY-382 during Cycle 1 or have an adverse event (AE) or other event as described in Protocol Section 9.3. The binomial probabilities of observing a DLT in a cohort of 6 and 9 patients, assuming a true rate of 33%, are provided in [Table 1](#) and [Table 2](#), respectively.

**Table 1: Binomial Probabilities of Dose-Limiting Toxicity in a Cohort of 6 Patients**

K	Binomial Probability		
	Exactly k DLTs	≤ k DLTs	>k DLTs
0	0.0878	0.0878	0.9122
1	0.2634	0.3512	0.6488
2	0.3292	0.6804	0.3196
3	0.2194	0.8998	0.1002
4	0.0823	0.9821	0.0179
5	0.0165	0.9986	0.0014
6	0.0014	1.0000	0.0000

DLT = dose-limiting toxicity; k = number of dose-limiting toxicities

**Table 2: Binomial Probabilities of Dose-Limiting Toxicity in a Cohort of 9 Patients**

K	Binomial Probability		
	Exactly k DLTs	≤ k DLTs	>k DLTs
0	0.0260	0.0260	0.9740
1	0.1171	0.1431	0.8569
2	0.2341	0.3772	0.6228
3	0.2731	0.6503	0.3497
4	0.2048	0.8552	0.1448
5	0.1024	0.9576	0.0424
6	0.0341	0.9917	0.0083
7	0.0073	0.9990	0.0010
8	0.0009	0.9999	0.0001
9	0.0001	1.0000	0.0000

DLT=dose-limiting toxicity; k=number of dose-limiting toxicities

For the Phase 2 PD-1/PD-L1 Inhibitor Refractory cohort, the sample size of approximately 20 patients will be evaluated for initial evidence of activity in this PD-1/PD-L1 refractory population.

For the Phase 2 prOVCA cohort, a Simon’s 2-stage optimal design (Simon 1989) will be used in the MSS/MMR-proficient prOVCA population. The null hypothesis of the true response rate is

15% will be tested at one-sided type I error rate of 10%. The alternative hypothesis is the true response rate is at least 35%. Accrual of patients in Stage 1 will continue until 9 evaluable MSS/MMR-proficient patients have been enrolled, with evaluable defined as having received at least one dose of study drug. The analysis for Stage 1 will not occur until all evaluable patients in Stage 1 have had the opportunity to have at least 2 post-baseline tumor assessments (or have discontinued tumor assessments beforehand). If there are fewer than 2 responders in these 9 patients, enrollment into this cohort of the study will be stopped. Otherwise, 14 additional patients will be accrued during Stage 2, for a total of 23 patients enrolled in this cohort. The null hypothesis will be rejected if 6 or more responses are observed in 23 patients. With this sample size, the actual Type I error is 9.9%, and the power is 80%. If the null hypothesis is true, the expected sample size is 15 patients, and the probability of stopping enrollment into this cohort of the study early is 60%. Patients who are MSI-H/mismatch repair-deficient (dMMR) will not be included in the Simon's 2-stage analyses and the study will ensure that the sample size requirements are met by enrolling the required number of MSS/MMR-proficient pOVCA patients.

For the Phase 2 PDA cohort, a Simon's 2-stage optimal design ([Simon 1989](#)) will be used in the MSS/MMR-proficient PDA population. The null hypothesis of the true response rate is 4%, versus alternative of 15%. Accrual of patients in Stage 1 will continue until 15 evaluable MSS/MMR-proficient patients have been enrolled, with evaluable defined as having received at least one dose of study drug. The analysis for Stage 1 will not occur until all evaluable patients in Stage 1 have had the opportunity to have at least 2 post-baseline tumor assessments (or have discontinued tumor assessments beforehand). If there are no responders in these 15 patients, enrollment into this cohort of the study will be stopped. Otherwise, 14 additional MSS/MMR-proficient patients will be accrued during Stage 2, for a total of 29 patients enrolled in this cohort. The null hypothesis will be rejected if 3 or more responses are observed in 29 MSS/MMR-proficient patients. With this sample size, the actual Type I error is 9.9%, and the power is 80%. If the null hypothesis is true, the expected sample size is 21 patients, and the probability of stopping enrollment into this cohort of the study early is 54%. PDA patients who are MSI-H/dMMR will not be included in the Simon's 2-stage analyses and the study will ensure that the sample size requirements are met by enrolling the required number of MSS/MMR-proficient PDA patients.

## 4.0 STUDY ENDPOINTS

### 4.1 Primary Endpoint

#### Phase 1b/Part A:

- Incidence of dose limiting toxicity (DLT), as a function of the dose of ARRY-382 when administered in combination with pembrolizumab

#### Phase 2: PD-1 or PD-L1 Inhibitor Refractory:

- Objective response rate (ORR), per RECIST v 1.1, as determined by the Investigator

#### Phase 2: Platinum-resistant Ovarian Cancer:

- ORR, per RECIST v 1.1, as determined by the Investigator

#### Phase 2: Pancreatic Ductal Adenocarcinoma:

- ORR, per RECIST v 1.1, as determined by the Investigator

### 4.2 Secondary Endpoints

#### Phase 1b/Part A:

- ORR, as determined by the Investigator
- Duration of response (DOR), as determined by the Investigator
- Progression-free survival (PFS), as determined by the Investigator
- Overall survival (OS)
- Immune-related response (irRR), as determined by the Investigator
- Immune-related progression-free survival (irPFS), as determined by the Investigator
- Type, frequency, and severity of AEs, using the National Cancer Institute (NCI) Common Terminology Criteria for Adverse Events (CTCAE)
- Serious adverse events (SAEs), using the NCI CTCAE
- Clinical laboratory values
- Vital signs
- Plasma concentration-time profiles
- PK parameters (e.g., area under the plasma concentration-time curve over the dosing interval  $[AUC_T]$ , maximum observed plasma concentration  $[C_{max}]$ , time of maximum observed plasma concentration  $[T_{max}]$ , plasma concentration measured just before the

next dose of study drug [ $C_{\text{trough}}$ ], accumulation ratio, and metabolite- to-parent ratio) for ARRY-382 and its metabolites, AR00469099, AR00469100, and AR00470870

Phase 2: PD-1 or PD-L1 Inhibitor Refractory:

- DOR, per RECIST v1.1, as determined by the Investigator
- PFS, per RECIST v1.1, as determined by the Investigator
- irRR, per irRC, as determined by the Investigator
- irPFS, per irRC, as determined by the Investigator
- OS
- Type, frequency, and severity of AEs, using the NCI CTCAE
- SAEs, using the NCI CTCAE
- Clinical laboratory values
- Vital signs
- Plasma concentration-time profiles
- PK parameters (e.g.,  $AUC_{\tau}$ ,  $C_{\text{max}}$ ,  $T_{\text{max}}$ ,  $C_{\text{trough}}$ , accumulation ratio, and metabolite-to-parent ratio) for ARRY-382 and its metabolites, AR00469099, AR00469100, and AR00470870

Phase 2: Platinum-resistant Ovarian Cancer:

- DOR, per RECIST v1.1, as determined by the Investigator
- PFS, per RECIST v1.1, as determined by the Investigator
- irRR, per irRC, as determined by the Investigator
- irPFS, per irRC, as determined by the Investigator
- OS
- Changes from baseline in relevant tumor markers
- Type, frequency, and severity of AEs, using the NCI CTCAE
- SAEs, using the NCI CTCAE
- Clinical laboratory values
- Vital signs
- Plasma concentration-time profiles

- PK parameters (e.g.,  $AUC_{\tau}$ ,  $C_{max}$ ,  $T_{max}$ ,  $C_{trough}$ , accumulation ratio, and metabolite-to-parent ratio) for ARRY-382 and its metabolites, AR00469099, AR00469100 and AR00470870

Phase 2: Pancreatic Ductal Adenocarcinoma:

- DOR, per RECIST v1.1, as determined by the Investigator
- PFS, per RECIST v1.1, as determined by the Investigator
- irRR, per irRC, as determined by the Investigator
- irPFS, per irRC, as determined by the Investigator
- OS
- Type, frequency, and severity of AEs, using the NCI CTCAE
- SAEs, using the NCI CTCAE
- Clinical laboratory values
- Vital signs
- Plasma concentration-time profiles
- PK parameters (e.g.,  $AUC_{\tau}$ ,  $C_{max}$ ,  $T_{max}$ ,  $C_{trough}$ , accumulation ratio, and metabolite-to-parent ratio) for ARRY-382 and its metabolites, AR00469099, AR00469100, and AR00470870

[REDACTED]

[REDACTED]

[REDACTED]

[REDACTED]

[REDACTED]

[REDACTED]

[REDACTED]

[REDACTED]

**C**  
**C**  
**I**  
[Redacted text block containing multiple lines of blacked-out content]

## 5.0 ANALYSIS SETS

### 5.1 Screened

Screened patients include all patients who sign the Informed Consent Form (ICF).

### 5.2 Dose-Determining Set

The dose-determining set (DDS) includes all patients in Phase 1b who receive at least 67% of the planned cumulative dose of ARRY-382 during Cycle 1 or discontinue the treatment because of DLT.

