	
carcinoma (HNSCC), bladder cancer, metastatic colorectal cancer (CRC), PDA, or gastric cancer. Patients who had prior treatment with an immune CPI (e.g., programmed cell death receptor 1 [PD-1], PD-L1, or cytotoxic T-lymphocyte antigen 4 [CTLA-4] inhibitor) will be excluded. Prior treatment with ipilimumab administered as adjuvant therapy in patients with melanoma is allowed. Prior treatment with a CSF-1R or CSF-1 (or macrophage colony-stimulating factor [MCSF]) inhibitor is allowed.
 
The Phase 2 PD-1/PD-L1 Inhibitor Refractory cohort will consist of up to 20 patients with advanced solid tumors who progressed on a PD-1/PD-L1 inhibitor-containing regimen as their most recent prior line of therapy. If clinical activity is observed, enrollment may be focused to include up to 10 additional patients with particular tumor histologies of interest.
 
The Phase 2 prOVCA cohort will consist of approximately 23 patients with prOVCA who are naïve to prior CPI therapy. The Phase 2 PDA cohort will consist of approximately 29 patients with PDA who have had at least one prior therapy who are naïve to prior CPI therapy.

Duration of Study Participation
	
Each phase of the study consists of a 28-day screening period; 21-day treatment cycles with the combination of ARRY-382 and pembrolizumab until disease progression as determined by the Investigator, unacceptable toxicity, withdrawal of consent, or death (or other discontinuation criteria are met); and a 30-day safety follow-up period.
 
Patients will be monitored for OS until 1 year after the date of the last patient’s first visit.

Statistical Considerations
	
For Part A, the sample size of approximately 18 evaluable patients (i.e., 6 to 9 patients in each dose cohort) is standard for purposes of determining the MTD and RP2D. Patients will be considered evaluable if they complete Cycle 1 or discontinue treatment due to DLT during Cycle 1.
 
For the Phase 2 PD-1/PD-L1 Inhibitor Refractory cohort, the sample size of up to 20 patients will be evaluated for initial evidence of activity in this PD-1/PD-L1 inhibitor-refractory population.
 
For the Phase 2 prOVCA cohort, a Simon’s 2-stage optimal design will be used in the MSS/MMR-proficient prOVCA population. The null hypothesis of the true response rate is 15%, versus alternative of 35%. Accrual of patients in Stage 1 will continue until 9 evaluable

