4.2 Dose-Limiting Toxicities (Part A)

For Part A, DLTs are defined as a treatment-emergent adverse event (TEAE) or abnormal laboratory value not clearly attributable to an extraneous cause, such as disease progression, intercurrent illness, or concomitant medications occurring during Cycle 1 and meeting one of the criteria shown in [Table 7](#).

Table 7: Dose-Limiting Toxicities (Part A)

Toxicity	DLT Definition Criteria
Nonhematologic AEs	
 • Recurring Grade 2 pneumonitis • Grade 3 irAE that does not resolve or return to baseline with immunosuppressive therapy within 28 days of onset • Grade 3 QTcF prolongation or > 60 msec increase in QTcF over baseline • Grade 3 rash that does not resolve or return to baseline in <10 days with symptomatic management • Any other Grade 3 or 4 nonhematologic AE, with the following exceptions: 
 ○ Alopecia ○ Grade 3 nausea, diarrhea, or vomiting lasting less than 72 hours with optimal medical management ○ Grade 3 AE of tumor flare or pseudoprogression (defined as local pain, irritation, or rash localized at sites of known or suspected tumor) ○ Grade 3 endocrinopathy that is adequately controlled by hormonal replacement

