Hematology AEs/ Laboratory abnormalities	
 • Any Grade 4 hematologic AEs or Grade 4 laboratory abnormalities, with the following exceptions: 
 ○ Grade 4 lymphopenia ○ Grade 4 neutropenia lasting ≤ 48 hours that is not associated with fever or other clinically significant symptoms ○ Isolated Grade 4 electrolyte imbalances/abnormalities that are not associated with clinical sequelae and are corrected with supplementation/appropriate management within 72 hours of onset • Grade 3 thrombocytopenia with clinically significant bleeding that requires platelet transfusion • Febrile neutropenia defined as a fever with or without clinically or microbiologically documented infection with absolute neutrophil count (ANC) < 1.0 × 10⁹/L, and a fever ≥ 38.5 °C • Any Grade 4 AST or ALT elevation unless clearly attributable to disease progression • Grade 3 AST or ALT elevation lasting > 7 days unless clearly attributable to disease progression • Grade 3 AST or ALT elevation associated with bilirubin levels ≥ 2 × ULN or an international normalized ratio (INR) > 1.5 unless clearly attributable to disease progression • Any Grade ≥ 3 bilirubin elevation unless clearly attributable to disease progression • CK elevation ≥ Grade 3 lasting > 7 days OR associated with an increase in creatinine ≥ 1.5 × the baseline value for creatinine
Dose delay	
 • Interruption of dosing for greater than 14 days, if due to AEs not related to the underlying disease or intercurrent illness
Other	
 • Inability to receive at least 67% of protocol-specified doses of ARRY-382 during Cycle 1 due to AEs not related to the underlying disease or intercurrent illness

AE = adverse event; ALT = alanine aminotransferase; ANC = absolute neutrophil count; AST = aspartate aminotransferase; CK = creatine kinase; DLT = dose-limiting toxicity; INR = International Normalized Ratio; irAE = immune-related adverse event; QTcF = QT interval corrected for heart rate using Fridericia's formula; ULN = upper limit of normal

For the purposes of dose escalation and determination of the MTD in Part A, only DLTs that occur during Cycle 1 will be necessarily considered for decisions regarding dose escalation. Other clinically significant toxicities or TEAEs that meet the definition of DLT occurring after Cycle 1 (i.e., dose-modifying events) may be considered when determining the RP2D.

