In Part A, patients who require a dose interruption or reduction during the initial 21-day treatment period (Cycle 1) will remain evaluable for tolerability decisions if the reason for the reduction and/or interruption represents a DLT. Patients will be replaced if they have received less than 67% dose intensity [(administered dose in mg/planned dose in mg) x 100] of ARRY-382 or if they did not receive pembrolizumab for any reason other than an AE or abnormal laboratory value that is not related to disease, disease progression, intercurrent illness or concomitant medications/therapies before completing Cycle 1.

Dose modifications of study drug are described in [Section 6.3](#).

For Part A, after the last patient in a given cohort has completed 1 cycle of study treatment, the Sponsor Medical Monitor and Investigators will meet to review all safety data and decide whether to continue or halt dose escalation, expand individual dose levels to gain additional safety data, determine the MTD and/or RP2D, or explore other dose levels. In addition to end-of cohort meetings, safety meetings including the Sponsor Medical Monitor and Investigators will be scheduled periodically (e.g., every 4 weeks) during the conduct of Phase 2 to review safety data for ongoing patients and patients who are being monitored during the follow-up period.

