9.3 Replacement of Patients

For Part A, patients will be replaced if they have received less than 67% dose intensity [(administered dose in mg/planned dose in mg) × 100] of ARRY-382 or if they did not receive pembrolizumab for any reason other than an AE or abnormal laboratory value that is not related to disease, disease progression, intercurrent illness or concomitant medications/therapies before completing Cycle 1.

For the Phase 2 PD-1/PD-L1 Inhibitor Refractory cohort, patients who discontinue prior to study completion will not be replaced.

For the Phase 2 prOVCA and PDA cohorts, additional patients will be enrolled to account for those who are found to be MSI-H/dMMR in order to evaluate the targeted patient population and to satisfy the Simon's 2-stage design.

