11.1.1 Sample Size

Overall, approximately 90 patients are planned for enrollment.

For Part A, the sample size of approximately 18 evaluable patients (i.e., 6 to 9 patients in each dose cohort) is standard for purposes of determining the MTD and RP2D. Patients will be considered evaluable if they receive at least 67% of protocol-specified doses of ARRY-382 during Cycle 1 or have an AE or other event as described in [Section 9.3](#). The binomial probabilities of observing a DLT in a cohort of 6 and 9 patients, assuming a true rate of 33%, are provided in [Table 12](#) and [Table 13](#), respectively.

Table 12: Binomial Probabilities of Dose-Limiting Toxicity in a Cohort of 6 Patients

K	Binomial Probability		
	Exactly k DLTs	≤ k DLTs	>k DLTs
0	0.0878	0.0878	0.9122
1	0.2634	0.3512	0.6488
2	0.3292	0.6804	0.3196
3	0.2194	0.8998	0.1002
4	0.0823	0.9821	0.0179
5	0.0165	0.9986	0.0014
6	0.0014	1.0000	0.0000

DLT = dose-limiting toxicity; k = number of dose-limiting toxicities

Table 13: Binomial Probabilities of Dose-Limiting Toxicity in a Cohort of 9 Patients

K	Binomial Probability		
	Exactly k DLTs	≤ k DLTs	>k DLTs
0	0.0260	0.0260	0.9740
1	0.1171	0.1431	0.8569
2	0.2341	0.3772	0.6228
3	0.2731	0.6503	0.3497
4	0.2048	0.8552	0.1448
5	0.1024	0.9576	0.0424
6	0.0341	0.9917	0.0083
7	0.0073	0.9990	0.0010
8	0.0009	0.9999	0.0001
9	0.0001	1.0000	0.0000

DLT=dose-limiting toxicity; k=number of dose-limiting toxicities

For the Phase 2 PD-1/PD-L1 Inhibitor Refractory cohort, the sample size of approximately 20 patients will be evaluated for initial evidence of activity in this PD-1/PD-L1 refractory population.

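### The SAP's Dose-Determining Set can leave out a patient who had a Cycle 1 DLT, and the SAP ties no analysis and no DLT table to that set

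*SAP*

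**What the plan says.** SAP 5.2 gives two ways into the DDS: "at least 67% of the planned cumulative dose of ARRY-382 during Cycle 1 or discontinue the treatment because of DLT". A patient under 67% therefore gets in only by stopping treatment.

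Evaluability in Part A is worded differently elsewhere:

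- Protocol 4.2: a patient with a Cycle 1 interruption or reduction "will remain evaluable for tolerability decisions if the reason for the reduction and/or interruption represents a DLT". Stopping treatment is not required.
- Protocol synopsis, Statistical Considerations: "Patients will be considered evaluable if they complete Cycle 1 or discontinue treatment due to DLT during Cycle 1".
- Protocol 11.1.1: at least 67% of ARRY-382 doses "during Cycle 1 or have an AE or other event as described in" Protocol 9.3. SAP 3.2 repeats this: "or have an adverse event (AE) or other event as described in Protocol Section 9.3".
- Protocol 9.3, with the same sentence in 4.2: patients are replaced if they fall under 67% dose intensity "or if they did not receive pembrolizumab for any reason other than an AE or abnormal laboratory value" of a stated kind. The sentence does not show whether the AE exception also covers the under-67% limb.

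Two entries in Protocol Table 7 matter here. One is broad: "Any other Grade 3 or 4 nonhematologic AE, with the following exceptions". The other makes a dosing shortfall a DLT: "Inability to receive at least 67% of protocol-specified doses of ARRY-382 during Cycle 1 due to AEs" that are unrelated to the underlying disease or an intercurrent illness.

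On analysis, SAP 4.1 names DLT incidence by ARRY-382 dose as the Phase 1b primary endpoint. Protocol 11.1.6 promises DLT incidence tables and a Part A DLT listing, in a section covering all treated patients. SAP 5.4 and 7.6 make the Safety Set the default for safety analyses. SAP 6.0 declares no changes from the protocol.

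**The concern.** A set built for dose determination should contain every patient whose Cycle 1 toxicity informed the dose decision. This one has a route by which a DLT patient drops out, and every patient lost by that route has a DLT. A rate computed on the set would be understated by that route.

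The SAP also does not say which set the primary-endpoint rate uses. If the Safety Set applies by default, no DLT is lost, but the denominator can include treated patients without a DLT who were not evaluable, and that also lowers the rate. With six or seven patients per dose level, moving one patient is visible. At stake is the reported Phase 1b primary-endpoint rate, not a dose decision.

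**Working it through.** **1. The plan's own figure.** Protocol Table 12 (SAP Table 1) gives 0.3512 for at most one DLT in 6 patients. At a true rate of 1/3: (2/3)^6 + 6 × (1/3) × (2/3)^5 = 64/729 + 192/729 = 256/729 = 0.3512. It reproduces, so the sample-size tables are not in question.

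**2. How a DLT patient falls below 67%.** The general Grade 3 row of Protocol Table 8 describes withholding ARRY-382 and then resuming one level lower. Assume, for illustration, a 300 mg patient dosed on Days 1–7, held on Days 8–14 and given 200 mg on Days 15–21:

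- Planned: 300 × 21 = 6300 mg; 67% of this is 4221 mg.
- Received: 7 × 300 + 7 × 200 = 3500 mg; 3500/6300 = 55.6%.

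Protocol 6.3.2 refers Part A reductions to Table 6 (levels 100, 200 and 400 mg) and also speaks of 100 mg steps. From 300 mg both give 200 mg. From 400 mg they give different levels, and those statements need reconciling. The Table 7 shortfall DLT reaches the same place directly: a patient under 67% of doses, none above the planned dose, is also under 67% of cumulative milligrams.

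**3. That patient under each rule.** The patient has a Cycle 1 DLT, received 55.6% of the dose and pembrolizumab, reached the end of Cycle 1 and did not discontinue.

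| Rule | Counted? |
|---|---|
| Protocol 4.2, DLT sentence | Yes |
| Protocol synopsis | Yes, if finishing the cycle on reduced dosing counts as completing it |
| Protocol 11.1.1 / SAP 3.2, by way of 9.3 | Only if the AE exception covers the under-67% limb |
| SAP 5.2 (DDS) | No |
| SAP 5.4 (Safety Set) | Yes |

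SAP 3.2 and SAP 5.2 are worded differently within one document.

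**4. What is attached to the DDS.** SAP 7.2 summarizes and lists membership of every analysis set, the DDS included. Otherwise efficacy uses the Full Analysis Set, safety the Safety Set and PK the Pharmacokinetic Set. None of the 20 summary tables in SAP 7.6.4 is for DLTs, nor is any listing there, and DLT does not appear in the unredacted text of SAP Section 7. Redaction is an unlikely explanation, because the contents list runs unbroken from 7.6.1 to 7.6.12 with no DLT section.

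**5. Size.** Protocol 2.3.1 reports 6, 7 and 6 patients treated at 200, 400 and 300 mg, with 2 DLT patients at 400 mg and 1 at 300 mg. Intervals are Clopper-Pearson 95%.

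| Dose | Denominator | Rate | 95% CI |
|---|---|---|---|
| 300 mg | All treated | 1/6 = 16.7% | 0.4–64.1% |
| 300 mg | DDS, DLT patient dropped (assumed) | 0/5 = 0% | 0–52.2% |
| 400 mg | All treated | 2/7 = 28.6% | 3.7–71.0% |
| 400 mg | One non-DLT patient non-evaluable (assumed) | 2/6 = 33.3% | 4.3–77.7% |

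The two doses illustrate different mechanisms: loss of a DLT patient from the DDS, and a non-evaluable patient in the Safety Set. They should not be joined into one range.

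**The case against.** The strongest reply is that the documents do supply a denominator. SAP 5.4 and 7.6 default to the Safety Set, Protocol 11.1.6 places the DLT tables in a section on all treated patients, and SAP 1.0 says to read the SAP with the protocol. On that reading the DDS limb changes no planned number, the DLT outputs are still owed under the protocol, and the set-membership listing would expose anyone caught between definitions. This stands in part: the primary endpoint is not left without any denominator. It does not explain why a set named for dose determination has no use, or why its rule can exclude a DLT.

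Several stronger readings are tempting and are not supported:

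- **That a DDS rate can only be too low.** This holds for the discontinuation limb alone. Assume a patient without a DLT takes 400 mg on Days 1–4, nothing on Days 5–6 and 200 mg on Days 7–21. That is 4 × 400 + 15 × 200 = 4600 of 8400 mg, or 54.8%, but 19 of 21 doses. A rule that counts doses, or a wide reading of the 9.3 exception, could keep this patient evaluable. The DDS would not, and leaving the patient out raises the rate.
- **That the 400 mg rate could fall to 1/6.** Nothing points to such a patient. Footnote a of Table 8 limits holding for CK, and the aminotransferase-with-bilirubin case may fall under a row listing discontinuation, which would put that patient in the DDS. The hepatic rows were added in Version 3, after Part A enrollment was complete, so the text those patients followed is not available here.
- **That the seventh patient at 400 mg was a replacement.** The protocol also allows a cohort to expand to 9.
- **That the dose selection is in doubt.** It was made under Protocol 4.2 and is complete.

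The SAP cites Protocol Version 5 and the comparison uses Version 4, so a later wording change cannot be excluded. The difference between SAP 3.2 and 5.2 and the missing DLT outputs do not depend on the version.

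**Conclusion.** The point holds as a defect in the analysis plan. As written, SAP 5.2 can exclude a Phase 1b patient with a Cycle 1 DLT who stayed on treatment, contrary to Protocol 4.2. The SAP neither assigns an analysis to that set nor specifies the DLT table and listing that Protocol 11.1.6 promises for the primary endpoint.

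The possible effect is one patient's weight in cohorts of six or seven: 16.7% to 0% at 300 mg if the DLT patient was under 67% and did not discontinue and, separately, 28.6% to 33.3% at 400 mg if one patient without a DLT was non-evaluable. Both conditions are assumptions; the documents show neither. The second figure is no longer below the 33% in Protocol 4.1, but this decides nothing, because the MTD/RP2D of 300 mg is already set. The matter should be corrected before database lock. It is a reporting issue.

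**What to change.** - **SAP 5.2:** define the DDS as every Phase 1b patient with a Cycle 1 DLT, regardless of dose received or discontinuation, plus patients without a DLT who received at least 67% of planned Cycle 1 ARRY-382 and meet the remaining evaluability conditions once Protocol 4.2 and 9.3 are reconciled.
- **SAP 7.6:** name the DDS as the denominator for a table of DLT incidence by dose level. The Safety Set rate can be shown beside it. Add the Part A DLT listing.
- **Wording:** reconcile evaluability across the synopsis, Protocol 4.2, 9.3 and 11.1.1, and SAP 3.2 and 5.2. State which limb the AE exception in 9.3 covers and whether 67% counts doses or milligrams. Record the choice in SAP 6.0, and check it against Protocol Version 5.

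The cost is SAP wording, one derivation, one table and one listing. No new data are needed.
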